### Secondary Outcomes (between and within-group comparisons will be used for each outcome):

- 1) Mean and standard deviation (SD) of change in NRS pain score at 1, 2, 3, 4, 5, 6, 24, 48, 72, 96, 120 hours post-saline and lidocaine injections
- 2) Mean and SD of average daily steps recorded at 24, 48, 72, 96, 120 hours post-saline and lidocaine injections (via Modus StepWatchTM or Evolution EvoWalkTM)

STU#:

- 3) Mean and SD of change in Orthotics and Prosthetics User's Survey (OPUS) score immediately post-injection and conclusion of washout (5 days) in saline and lidocaine groups
- 4) Mean and SD of change in Groningen Activity Restriction Scale (GARS) score immediately post-injection and conclusion of washout (5 days) in saline and lidocaine groups
- 5) General linear model analysis of the interaction between crossover sequence
- 6) Demographic factors associated with large improvement in NRS pain score
- 7) Complications associated with the procedures

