### *Devices*

During initial evaluation (visit 1), participants' prostheses will be fit with a Modus StepWatch™ or Evolution EvoWalk™. This will be tested in clinic by a research coordinator to ensure proper step count. The device will remain on participant's prosthesis until study completion. Participant kinematic and gait data will be recorded by Modus StepWatch™ or Evolution EvoWalk™ and uploaded via Bluetooth to secure a de-identified, Health Insurance Portability and Accountability Act (HIPAA) compliant cloud-based storage application and extracted by research coordinator to an encrypted, HIPAA-compliant, Northwestern research database (REDCap).

Participants will also be instructed to maintain a daily pain log through My Pain Diary smartphone application or paper log depending on participant preference. They will be asked to log daily pain scores during their treatment. Data will be extracted by a researcher to an encrypted, HIPAA-compliant, Northwestern research database (REDCap).

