### *Visit 2 (procedure 1)– Randomization and Study Intervention*

STU#:

Eligible participants will return to the Lavin 14th floor Pain clinic within 2 weeks of the initial visit. Participants will be randomized to treatment or sham group. Participant pre-procedure 1 NRS pain score will be collected. Individual pain log will start 15 minutes after procedure. Participant will log pain score every hour until asleep. The next day, participant will record daily NRS pain score for 5 days.

Randomization

A computer-generated 1:1 block randomization scheme (<https://www.randomizer.org>) will be used to assign participants to receive a peri-sciatic nerve injection with either 10 mL of 2% lidocaine or 10 mL of preservative-free saline (compounded by the 11th floor Lavin pharmacy and labeled with a “1” or “2” to ensure adequate blinding). Randomization will be performed by a research assistant by opening an opaque envelope to reveal the participant number and group assignment printed inside of the envelope. This will instruct authorized study personnel to draw up either 2% lidocaine or saline (labeled “1” or “2” by compounding pharmacy per above). The blinded injectionist will be provided an unlabeled syringe of injectate immediately before the injection procedure. Participants, injectionist, and study personnel who collect outcomes data will be blinded to group assignment.

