Treatment block of sciatic nerve in contralateral limb: Procedure planning will be based on the participant’s indication of residual limb point of maximal pain (measured by distance from posterior superior iliac spine (PSIS) to most painful point [in cm]). Note that this point may beyond the anatomic end of the residual limb. The block will be performed at the exact same distance from PSIS on the contralateral side. If the block cannot be performed at this site due to anatomic or technical considerations (such as proximity to vascular structures), a more cephalad site along the sciatic nerve course will be selected for the procedure. During the block procedure, the participant will be positioned prone. Standard American Society of Anesthesiologists (ASA) procedure monitoring will be used (pulse oximetry, ECG, blood pressure, and heart rate). The participant’s skin will be prepared with chlorhexidine. A sterile ultrasound probe will be placed on the participants’ residual limb at a transverse angle in order to view the nerve in short-axis. The skin will be anesthetized with 1-2 mL of 1.0% lidocaine. The ultrasound probe (in plane) will be advanced to the intact limb’s sciatic nerve equidistance to that of the residual limb point of maximal pain. A 22-gauge standard echogenic needle will be placed adjacent to the sciatic nerve with ultrasound guidance. At the site of the nerve, 10mL of 2% lidocaine will be injected through the needle in the intervention group and 10ml of saline will be injected in the sham group.

In treatment group: At the site of the nerve, 10mL of 2% lidocaine will be injected through the needle

In control group: At the site of the nerve, 10ml of saline will be injected through the needle

Following injection, participants will be kept in recovery area and monitored for 30 minutes. They will also complete a pain log starting 15 minutes post-injection. After the first pain score is recorded, the participants will dress and exit procedure area. Participants will be required to arrange transportation as the block may impair lower extremity motor function.

Both saline and local anesthetic will be administered to all subjects with a crossover design as described above. Participants will undergo 5-day washout between injections.

*Visit 3 – Crossover for both groups*

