Eligible participants will return to the Lavin 14th floor Pain clinic within 5 days of visit 2. Participant pre-procedure 2 NRS and OPUS will be collected. Note that this will serve as post-procedure 1 washout and pre-procedure 2 intervention data point.

Both groups: will cross over and undergo treatment as described in *Visit 2*. Participant pain log will start 15 minutes after procedure 2. Participant will log pain scores every hour until asleep. The next day, participant will record daily NRS pain score for 5 days.

*Telephone call 1,2,3:* participant will be called at 1- and 5-days post-procedures for NRS, OPUS survey and safety monitoring by research coordinator (see Safety Monitoring below).

**SAFETY MONITORING** Participants will be contacted one day following both interventions to assess for any adverse events or side effects.

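### The 120-hour step value after injection 1 can include time after injection 2; this leaves half the injection-day step difference in the treatment comparison, in a direction the documents do not settle

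*Combined protocol and SAP*

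**What the plan says.** Under Study Endpoints, Secondary Outcomes, item 2 is "Mean and SD of average daily steps recorded at 24, 48, 72, 96, 120 hours post-saline and lidocaine injections", with comparisons planned between and within groups. The section does not say whether a daily value is a calendar-day total, a 24-hour block counted from the injection, or an average over several days.

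The rest of the schedule is under Procedures Involved:

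- Devices: "The device will remain on participant's prosthesis until study completion".
- End of the procedure description for Visit 2: "Participants will undergo 5-day washout between injections".
- Visit 3 (crossover): "Eligible participants will return to the Lavin 14th floor Pain clinic within 5 days of visit 2". This sets a latest day but no earliest one.
- Diary, after each injection: "The next day, participant will record daily NRS pain score for 5 days".
- Pain at Visit 3: "Participant pre-procedure 2 NRS and OPUS will be collected", followed by "Note that this will serve as post-procedure 1 washout and pre-procedure 2 intervention data point".
- After the block: "Participants will be required to arrange transportation as the block may impair lower extremity motor function".

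Neither the endpoint section nor the Statistical Plan says what happens to first-period step data recorded after injection 2.

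**The concern.** The fifth day after injection 1 is, at the latest, the day of injection 2. It can contain a clinic trip, a recovery period and hours spent under the other injectate. The fifth day after injection 2 contains none of these. The two 120-hour step values are therefore collected under different conditions but compared as if the conditions were the same.

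One might expect the crossover to balance this out. It does so only in part, because the contaminating injectate differs by sequence. In saline-first participants the saline value picks up the lidocaine procedure day. In lidocaine-first participants the lidocaine value picks up the saline procedure day. Whatever lidocaine does to walking on the injection day, relative to saline, is then credited to the wrong arm at 120 h.

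**Working it through.** **Plan's own figure.** The plan gives no figure for steps: no mean, SD, expected difference or power. Its only sample-size figure is N = 20, for the primary outcome, and nothing below depends on it.

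**Step 1: when the windows overlap.** Inputs are the five step time points (endpoint section), the nominal gap of 5 × 24 = 120 h (Visit 2) and the 5-day maximum (Visit 3).

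- *Calendar-day totals, Visit 3 on day 5.* The fifth total after injection 1 is the total for the day of injection 2.
- *24-hour blocks from injection.* Overlap of the 96–120 h block with time after injection 2 is 120 minus the hour of injection 2, limited to the range 0 to 24:

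| Injection 2 at (h after injection 1) | Hours of the 96–120 h block after injection 2 |
|---|---|
| 120 or later | 0 |
| 114 | 6 |
| 108 | 12 |
| 96 | 24 |

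At 72 h the 72–96 h block is also fully overlapped. Overlap is therefore zero only if both conditions hold: windows run from injection time, and the gap is at least 120 h. The plan secures neither.

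**Step 2: what remains in the treatment comparison.** Suppose a saline procedure day changes steps by −c, and a lidocaine procedure day by −c + L. L is the lidocaine-minus-saline injection-day difference. Assume no true effect at 120 h and a fifth-day value that carries the whole procedure-day shift. The lidocaine-minus-saline difference at 120 h is then:

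- lidocaine-first: (−c) − 0 = −c
- saline-first: 0 − (−c + L) = c − L

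With nA lidocaine-first and nB saline-first completers, the simple mean is [nB(c − L) − nA·c] / (nA + nB). With nA = nB this is −L/2, and c cancels.

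Illustrative values, assumed because the documents give none, with equal sequences:

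| L (steps) | Bias, lidocaine minus saline | If half the shift falls in the window |
|---|---|---|
| −500 (motor block dominates) | +250 | +125 |
| 0 | 0 | 0 |
| +500 (pain relief dominates) | −250 | −125 |

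**Step 3: imbalance and the period term.** If dropout leaves 8 lidocaine-first and 10 saline-first completers, c no longer cancels in the simple mean. With c = 1,000 and L = 0 it is (10 × 1,000 − 8 × 1,000)/18 = +111 steps; with the numbers reversed it is −111. A period-adjusted estimate weights the two sequence means equally: [−c + (c − L)]/2 = −L/2. The period term thus removes c but leaves −L/2, because that part is a treatment difference and not a period difference.

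**Step 4: if the value is an average.** If the 120-hour value averages all five days, a one-day effect is divided by five and the bias is −L/10: +50 steps at L = −500, or −50 at L = +500.

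**The case against.** **The endpoint is timed in hours after injection.** Read as 24-hour blocks, with a full 120-hour gap, there is no overlap. This stands as a possible reading, but the plan does not state it, and the Visit 3 wording permits a shorter gap. Under 24-hour blocks the problem reduces to that scheduling ambiguity. Under calendar-day totals it remains even when Visit 3 falls exactly on day 5.

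**Direction.** A reader might infer that the comparison is biased toward lidocaine, since the only injection-day effect on walking that the documents name is possible motor impairment. They do not support this as a conclusion. The Objectives section aims at functional improvement, and if pain relief raised same-day steps the bias would run the other way.

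**False-positive rates.** A reader might also want an inflated error rate. None can be given with authority. With assumed values c = 300, L = −1,000, an SD of within-person differences of 1,000 steps and 9 completers per sequence, a paired test rejects about 30% of the time under no true effect. The Statistical Plan names unpaired tests, and an unpaired t test on the same scenario rejects about 16% of the time at a within-person correlation of 0.5 and 6% at 0.7. The rate depends on undocumented inputs and on the test; the bias of +500 steps does not depend on the test.

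**Pain scores.** The diary is largely protected, because a score taken before procedure 2 is named as the end-of-washout value for injection 1. Only a fifth-day diary entry made after injection 2 would be contaminated. Relief from lidocaine would then improve the saline score and count against lidocaine.

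**Scope.** One of five step time points is exposed if Visit 3 falls on day 5. The 15-minute primary outcome is untouched.

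**Conclusion.** The concern holds in a limited form. As written, the plan allows the fifth-day step value after injection 1, but not after injection 2, to include time after the other injectate. With balanced sequences this leaves −L/2 in the 120-hour lidocaine-minus-saline comparison, and period adjustment does not remove it.

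The result assumes calendar-day totals, or a procedure 2 that starts before 120 h, and a value that reflects the fifth day alone. It shrinks with partial overlap or averaging and is zero if L is zero. Neither the sign nor the size of L can be taken from the documents. An earlier Visit 3 would widen the overlap and could reach earlier time points. This should be corrected before step data are analysed, because a window chosen afterwards would be a post hoc choice. It does not threaten the trial's main conclusion.

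**What to change.** 1. In Secondary Outcomes item 2, define each step value as the count in a 24-hour block starting at the injection time, and say whether each time point is a single block or an average over blocks.
2. Exclude first-period step data recorded after injection 2.
3. End the lidocaine–saline step comparison, in both periods, at the last window completed before the day of procedure 2. That is 96 h if Visit 3 falls on day 5. Report 120-hour steps descriptively by period. A fixed 96-hour cut alone would not protect against an earlier Visit 3, so items 2 and 3 are both needed.
4. For pain, name the pre-procedure-2 score as the first-period 120-hour value, and do not use a diary entry made after procedure 2.
5. Reconcile "Participants will undergo 5-day washout between injections" with the Visit 3 timing. The two passages should state one consistent interval.

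The cost is wording in the endpoint section and Statistical Plan, with no new visits, data or participants. One of the five step comparisons may be lost. The documents do not say whether the counter's export is time-stamped within the day. If only daily totals are available, the same rule limits the comparison to whole days lying between the two procedure days.

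### After the immediate score, OPUS and GARS are next compared only at the end of washout, where a working crossover expects no treatment difference, while the day-1 OPUS already collected is not listed as an outcome

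*Combined protocol and SAP*

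**What the plan says.** All references are to the combined protocol and SAP.

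- **Objectives.** The aim covers functional improvement as well as pain relief.
- **Secondary Outcomes, items 3 and 4.** Change in OPUS and in GARS is reported "immediately post-injection and conclusion of washout (5 days) in saline and lidocaine groups". The list heading adds that "between and within-group comparisons will be used for each outcome".
- **Secondary Outcomes, items 1 and 2.** Pain scores and daily steps each have a 24-hour point and run to 120 hours.
- **Visit 2, treatment block.** "Participants will undergo 5-day washout between injections".
- **Visit 3.** On timing: "Eligible participants will return to the Lavin 14th floor Pain clinic within 5 days of visit 2". On what is measured then: "Participant pre-procedure 2 NRS and OPUS will be collected". On the role of that score: "this will serve as post-procedure 1 washout and pre-procedure 2 intervention data point".
- **Telephone calls.** The "participant will be called at 1- and 5-days post-procedures for NRS, OPUS survey and safety monitoring by research coordinator".
- **GARS.** The Visit 1 text names it as a survey to complete, and the Data section lists it. The text for Visits 2 and 3 and the calls does not mention it.

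No section states how long the block's effect on pain or function is expected to last.

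**The concern.** Day 5 has two roles. In the crossover it is the time by which the effect of the first injection should have gone. In items 3 and 4 it is the only time after the immediate score at which lidocaine and saline are compared on the questionnaires. The better the washout works, the less this comparison can show.

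What is at stake is interpretation. A null day-5 questionnaire result is what the design expects, yet it could be reported as absence of functional benefit, and function is part of the aim. Meanwhile a day-1 OPUS, taken nearer the block and before the end of washout, is collected after each procedure with no stated use.

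**Working it through.** **1. Number of completers.** The plan gives no precision or power for OPUS or GARS. Its only sample size is for the primary outcome. From Power Analysis, the discordant proportions sum to 0.875 and differ by 0.625, so they are (0.875 + 0.625)/2 = 0.75 and (0.875 − 0.625)/2 = 0.125. The exact two-sided McNemar test has power 0.790 at n = 17 and 0.830 at n = 18. Then 18/(1 − 0.10) = 20, which reproduces the plan's figure. I use 18 completers below.

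**2. Listed outcomes against scheduled collection.**

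| Measure and time | Listed as outcome | Collection named in the schedule |
|---|---|---|
| OPUS, immediate | yes, item 3 | no |
| OPUS, day 1 | no | yes, telephone call |
| OPUS, day 5 | yes, item 3 | yes, Visit 3 and telephone call |
| GARS, immediate | yes, item 4 | no |
| GARS, day 1 | no | no |
| GARS, day 5 | yes, item 4 | no |
| Steps, 24 hours | yes, item 2 | yes, device on the prosthesis |

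**3. Expected treatment contrast.** Let d1, d5, d6 and d10 be the lidocaine-minus-saline effect remaining 1, 5, 6 and 10 days after an injection. Assume procedure 2 falls 5 days after procedure 1 and that period effects are additive, so they cancel. Average the period-1 and period-2 contrasts.

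- Day 5, raw score or change from Visit 1: period 1 gives d5. Period 2 gives d5 − d10, because those who had lidocaine first still carry d10. The mean is d5 − d10/2.
- Day 5, change from the last pre-injection OPUS: period 1 gives d5. In period 2, those now on lidocaine change by d5 and those now on saline change by d10 − d5, so the contrast is 2·d5 − d10. The mean is 1.5·d5 − d10/2.
- Complete washout (d5 = d10 = 0): both means are 0. The rejection rate is then alpha, 5%, at any N.
- Incomplete washout with d5 ≠ 0 and d10 = 0: the second version has expectation 1.5·d5, overstating the day-5 effect by half, because the Visit 3 baseline is contaminated.
- Day 1, change from the last pre-injection OPUS: the same steps give d1 + (d5 − d6)/2, which is d1 when the washout is complete.

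**4. Illustrative power.** The following are my assumptions and are not in the documents: an early effect of 1 SD of the within-person differences, exponential decay, and scores that reflect function at the time of asking. The fraction remaining is 2^(−t/half-life), with t = 24 or 120 hours. Power is for a two-sided 5% paired t test with n = 18, from the noncentral t with 17 degrees of freedom and noncentrality fraction × √18. Carry-over and baseline distortion are ignored.

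| Half-life (h) | Left at day 1 | Power, day 1 | Left at day 5 | Power, day 5 |
|---|---|---|---|---|
| 6 | 6.25% | 0.057 | under 0.1% | 0.050 |
| 12 | 25% | 0.170 | 0.1% | 0.050 |
| 24 | 50% | 0.516 | 3.1% | 0.052 |
| 48 | 70.7% | 0.807 | 17.7% | 0.109 |
| 96 | 84.1% | 0.919 | 42.0% | 0.391 |
| 120 | 87.1% | 0.935 | 50% | 0.516 |

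A smaller early effect lowers both power columns. With 0.7 SD, power is 0.80 if all of it is present at the time of asking, 0.29 if half is left, 0.11 if a quarter is left and 0.06 if a tenth is left.

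**The case against.** A reader might infer that the OPUS and GARS outcomes as a whole are null by design, or that function goes untested on day 1. The documents support neither reading.

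- Each item names two time points, and only one is the end of washout. Within-group change is also planned and can move with time or placebo response. The zero expectation applies to one between-treatment contrast, and only if the washout is complete.
- Item 2 records daily steps from 24 hours, so day-1 function is already an outcome. What is missing is a day-1 questionnaire outcome.
- Nothing is injected after period 2, so an effect lasting 5 days after procedure 2 contaminates no later measurement. In period 1 the day-5 score is a randomised comparison made before crossover. A difference there would be real evidence of a lasting effect as well as a warning about period 2. The benefits section allows for long-term improvement in pain.
- The power figures rest on assumed decay. At a 6-hour half-life day 1 is nearly as uninformative as day 5, and at 96 to 120 hours day 5 is not null. The documents give no recall period for either questionnaire. If a score covers the days since injection, the decay arithmetic does not apply.
- Following these measures to 5 days matches pain and steps and provides a useful washout check.

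All of this stands, and it limits the point to the day-5 treatment contrast. It gives no reason to leave the day-1 OPUS unlisted. The immediate score does not fill the gap well: no visit text schedules it, and the protocol itself warns that the block may impair leg motor function.

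**Conclusion.** The point holds in a limited form. Under the crossover's own assumption of complete washout, the day-5 lidocaine-saline contrast in OPUS and GARS has expectation zero. If the effect of procedure 1 has not gone, the Visit 3 OPUS is a contaminated baseline. Either way, this contrast is a weak test of functional benefit, and a null result there says little about what the block does on day 1.

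Its size cannot be fixed from the documents because no effect duration is given. Under the stated assumptions, power runs from about 0.06 to above 0.8 at day 1 and from 0.05 to about 0.52 at day 5. Day 1 has the higher power at every half-life shown, though the gain is negligible if the effect is very short. The logic of the zero contrast does not depend on these figures. These are secondary outcomes in a 20-person trial, and the primary analysis and sample size are untouched.

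**What to change.** 1. **Item 3 (OPUS).** Add change in OPUS at day 1 after each procedure, and name it the main post-block questionnaire comparison. State which pre-injection score the change is taken from. The data are already collected, so the cost is wording only.
2. **5-day OPUS.** Keep it, and say that it is interpreted mainly as a washout and carry-over check, so that a null result is not reported as no functional benefit.
3. **Item 4 (GARS).** Reconcile it with the schedule. No visit or call after Visit 1 names GARS, so neither time point in item 4 has a scheduled collection, and there is no scheduled 5-day GARS score to reinterpret. Adding GARS to the existing day-1 and day-5 contacts would cost a small amount of contact time.
4. **Washout timing.** The 5-day washout and a Visit 3 that may fall at any time up to 5 days after Visit 2 need to be reconciled, because the 5-day score depends on that interval.

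No change to N and no new visit is needed.

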## **STUDY ENDPOINTS:**

### Primary Outcome

Comparison of the proportions of participants reporting  $\geq 50\%$  improvement in NRS pain score from baseline at 15 minutes in treatment and sham groups

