## **POTENTIAL BENEFITS TO PARTICIPANTS**

Individual participants may experience short- or long-term improvements in pain as a result of participation in this research.

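### The plan's only crossover check cannot isolate carry-over, and the shared Visit 3 pain score can bias the 24–120 h NRS contrasts by up to 50% of the day-5 effect, in a direction set by an unstated baseline

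*Combined protocol and SAP*

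**What the plan says.** All references are to the combined protocol and SAP.

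- **Design (Procedures Involved, Visit 2).** "Both saline and local anesthetic will be administered to all subjects with a crossover design as described above". There are thus two sequences and two periods, allocated 1:1. "Participants will undergo 5-day washout between injections".
- **Visit 3.** Participants "return to the Lavin 14th floor Pain clinic within 5 days of visit 2". NRS and OPUS are taken before the second injection: "Note that this will serve as post-procedure 1 washout and pre-procedure 2 intervention data point".
- **Outcomes.** The primary is the proportion with at least 50% "improvement in NRS pain score from baseline at 15 minutes in treatment and sham groups". Secondary outcome 1 is "change in NRS pain score at 1, 2, 3, 4, 5, 6, 24, 48, 72, 96, 120 hours post-saline and lidocaine injections".
- **Crossover check.** Secondary outcome 5 reads, in full, "General linear model analysis of the interaction between crossover sequence". What sequence is to interact with is not stated.
- **Baseline.** The Power Analysis defines change for the primary from the pre-injection score of each condition. Secondary Outcomes does not say what the 24–120 h changes are measured from. Visit 1 also collects baseline outcome measures.
- **Statistical Plan.** NRS change is compared by an unpaired t test or Mann-Whitney test. No general linear model and no period, sequence or carry-over term appears there.
- **Potential Benefits to Participants.** "Individual participants may experience short- or long-term improvements in pain as a result of participation in this research".

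**The concern.** The crossover relies on the first injection having no effect left at Visit 3, while the secondary outcomes look for an effect at that same time, 120 h. If one is found, it is also carry-over into period 2. Because one score closes period 1 and opens period 2, a residual effect enters both periods' change scores.

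At stake are the 24–120 h contrasts, which are the only evidence the trial would have for relief outlasting the block. The one analysis that might warn of carry-over is unfinished, and however it is completed, it confounds carry-over with another effect. A null result would be weak reassurance, and a positive one could not be attributed to carry-over.

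**Working it through.** **The plan's own figure.** The Power Analysis gives a discordant difference of 0.625 and a discordant total of 0.875. The two discordant proportions are (0.875 + 0.625)/2 = 0.75 and (0.875 − 0.625)/2 = 0.125. An exact two-sided McNemar test has power 0.790 with 17 pairs and 0.830 with 18, and 18/0.9 = 20. The stated sample size reproduces. It matters here only because it fixes the numbers available: 18 to 20 people, about 10 per sequence.

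**What a sequence interaction measures.** Code sequence S (lidocaine-first +1), period P (first +1) and treatment T (lidocaine +1):

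| Cell | S | P | T | S×T | S×P |
|---|---|---|---|---|---|
| Lidocaine-first, period 1 | +1 | +1 | +1 | +1 | +1 |
| Lidocaine-first, period 2 | +1 | −1 | −1 | −1 | −1 |
| Saline-first, period 1 | −1 | +1 | −1 | +1 | −1 |
| Saline-first, period 2 | −1 | −1 | +1 | −1 | +1 |

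S×T equals P in every cell, and S×P equals T. Either completion of item 5 is therefore confounded with a main effect.

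**Bias at 120 h.** Assumptions (none given in the documents): equal sequences, no saline effect, no period effect, true lidocaine effect −r at 120 h, and a share w of that residual waning over the 120 h after Visit 3.

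*Own-period baseline:*
- Lidocaine-first: lidocaine −r, then saline +w·r.
- Saline-first: saline 0, then lidocaine −r.
- Lidocaine minus saline = −r − (w·r + 0)/2 = −r(1 + w/2).

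*Common Visit 1 baseline:*
- Lidocaine-first: lidocaine −r, then saline −(1 − w)r.
- Saline-first: saline 0, then lidocaine −r.
- Lidocaine minus saline = −r + (1 − w)r/2.

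| Share waned (w) | Own-period baseline | Common baseline |
|---|---|---|
| 0 | −1.00r (unbiased) | −0.50r (50% too small) |
| 0.5 | −1.25r (25% too large) | −0.75r (25% too small) |
| 1 | −1.50r (50% too large) | −1.00r (unbiased) |

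With r = 2 points, own-period baselines and full waning, the estimate is −3 instead of −2. At earlier times the own-baseline bias is half of whatever has waned by then. At 15 minutes almost nothing has waned.

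**Does the check respond?** With own-period baselines, the lidocaine-minus-saline contrast is −(1 + w)r in the lidocaine-first sequence and −r in the saline-first sequence. S×T therefore shifts by w·r: it responds to waning carry-over but cannot tell it from a period effect.

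**Power and precision.** Assume NRS SD 2, equal within-person correlation 0.6, 10 per sequence and t(18) = 2.101.
- *S×T on change scores with a shared Visit 3 score.* The per-person contrast is 2×(Visit 3) − first − last, with variance 6 × 4 × 0.4 = 9.6. SE = √(9.6 × 2/10) = 1.39. With full waning, power is about 11%, 28% and 54% for r = 1, 2 and 3.
- *Sequence main effect on raw totals.* With 18 completers and correlation 0.3 to 0.7, power is 19–24% for a carry-over of 1 SD.
- *Pre-procedure-2 minus pre-procedure-1 NRS, between sequences.* Variance 2 × 4 × 0.4 = 3.2. SE = √(3.2 × 2/10) = 0.80. The 95% CI half-width is 2.101 × 0.80 = 1.7 points. For correlation 0.3 to 0.7 it is 2.101 × √(8(1 − ρ) × 0.2), or 2.2 to 1.5 points. Power is about 22%, 66% and 94% for r = 1, 2 and 3.

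**Timing.** A 5-day washout and a visit within 5 days agree only if Visit 3 falls at the limit. If it is earlier, the period-1 score at 120 h is recorded after the second injection, and the Visit 3 score is no longer the last period-1 outcome.

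**The case against.** The strongest reply is that the check is not blind. Under full waning with own-period baselines, the treatment contrast is −2r in one sequence and −r in the other, so S×T moves. A model containing a sequence interaction would normally also contain the sequence main effect. On summed change scores that main effect reduces to last minus first score, and its half-width is the same 1.7 points as the proposed contrast. This stands. A reader might infer that no completion of item 5 could ever detect carry-over, or that the replacement is more precise. Neither is so. The replacement's advantage is that it is taken before the second injection and estimates the day-5 residual whether or not it later wanes. The summed-change effect equals w·r and vanishes if nothing wanes.

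A second reply is that nothing in the documents shows a residual at day 5. The hypothesis concerns immediate relief, the primary is at 15 minutes, and the benefits statement is generic. That also stands, and it is why the bias is conditional on r. But a plan that tests for an effect at 120 h cannot also take its absence for granted.

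A third reply is that the direction of bias depends on a baseline that Secondary Outcomes does not fix. This is correct, and it is part of the problem.

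**Conclusion.** The concern holds in limited form. Item 5 is incomplete, cannot isolate carry-over and has little power at this sample size, and no other planned analysis addresses carry-over or period. If relief r remains at Visit 3, the 120 h lidocaine-minus-saline effect is overstated by 0 to 50% with own-period baselines, or understated by 0 to 50% with a common Visit 1 baseline. These figures assume equal sequences, no saline effect and no period effect. If r is zero there is no such bias.

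A reader might infer that any lasting lidocaine effect is scored as worsening on sham. The documents do not support that: it happens only in the lidocaine-first sequence, only for the part that wanes after Visit 3, and only with own-period baselines. Nor do they support a bias that always favours lidocaine. The 15-minute primary is touched only through a possibly lower second baseline, with no fixed direction: a smaller drop meets the 50% threshold, but less pain is left to relieve. The point should be corrected, but it concerns the secondary outcomes and does not invalidate the primary.

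**What to change.** 1. Replace secondary outcome 5 with the between-sequence difference in (pre-procedure-2 NRS minus pre-procedure-1 NRS), with a 95% CI. Present it as an estimate of the residual at Visit 3.
2. For the 24–120 h outcomes, state the baseline used. Always report the period-1-only lidocaine-versus-saline difference with its 95% CI beside a crossover estimate that includes a period term. Do not make this conditional on a carry-over test. Where the Visit 3 score serves as the 120 h score, the period-1 comparison at 120 h is the same contrast as in step 1 and needs reporting only once.
3. Interpret any claim of effect at 24–120 h in light of the period-1 estimate, without a pass/fail rule.
4. Reconcile the washout statement with the Visit 3 window, and say how a 120 h score recorded after the second injection is handled.

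Steps 1 to 3 cost some SAP wording and one extra table, and they use NRS data already collected. The drawback is precision: the period-1 estimate compares about 10 people with 10, with a half-width near 1.7 NRS points under the assumed SD and correlation.
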